9.2 Study Design

To achieve comparable groups for known and unknown risk factors randomization will be performed as unistratified block randomization with random block sizes in a 1:1 allocation ratio. Allocation to treatment will be carried out by means of a computer-generated random study numbers with group assignment.

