9.3 Sample Size

Appropriate sample size is calculated based on assumption of difference of 20 percent in blood loss in favor of the Thunderbeat™ device as compared with conventional techniques. This difference is considered clinically relevant based on previous similar studies [9-11]. A sample size of 60 is considered sufficient to prove this difference, if present (alpha error set at 0.05, power>80 percent).

Approximately 100 patients per year undergo a Whipple procedure at Washington University Medical Center. The estimated time frame to enroll 60 patients is approximately 18 to 24 months.

The total expected enrollment is 60 patients: 30 Thunderbeat and 30 conventional.

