9.4 Data Analysis

Data analysis for this study will be descriptive in nature. Demographic and clinical characteristics of the sample, as well as intraoperative findings and post-surgery complications will be summarized using descriptive statistics. The incidences of surgical complications and procedure-related adverse events will be calculated, and the confidence intervals will also be provided.

Patients assigned to the Thunderbeat™ group will be compared with those who had conventional techniques using χ^2 tests for categorical variables and Student's t-tests for continuous variables. For the t-tests equal variances were not be assumed, unless significant by Levene's test. Mann-Whitney *U* tests will be utilized for non-normally distributed variables. Two-tailed *P* values 0.05 will be considered statistically significant.

Multivariate analyses for intraoperative blood loss (mL), operative time (minutes), postoperative morbidity (any grades 1–5 and major grades 3–5), and hospital length of stay (days) will be performed using binary logistic regression and linear regression models to examine the relationship between intervention groups and examined outcomes and to identify potential confounders. The results of multivariate analyses will be expressed as odds ratios with corresponding 95% confidence intervals. All analyses will be performed using SPSS 20.0 statistical software (SPSS Inc.Chicago, IL).

REFERENCES

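### Section 9.4 fits ordinary logistic models with no limit on covariates to morbidity in 60 patients; with about five covariates the device odds ratio becomes unstable and a true effect is exaggerated

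*Combined protocol and SAP*

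**What the plan says.** Section 9.4 lists five outcomes for multivariate modelling: blood loss, operative time, length of stay, and two binary ones, any-grade morbidity and major (grade 3–5) morbidity. These analyses "will be performed using binary logistic regression and linear regression models to examine the relationship between intervention groups and examined outcomes". A further stated aim is to find possible confounders, which implies several candidate covariates. On reporting: "The results of multivariate analyses will be expressed as odds ratios with corresponding 95% confidence intervals". An odds ratio applies only to the binary outcomes.

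No penalised or exact method is named, so ordinary maximum likelihood is the natural reading. Section 9.4 gives no covariate list, number, cap or selection rule, no expected morbidity rate, and no plan for sparse data or separation. It assigns all analyses to SPSS 20.0.

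The sample was sized for a different endpoint. Section 9.3 rests on an "assumption of difference of 20 percent in blood loss in favor of the Thunderbeat™ device", and states: "The total expected enrollment is 60 patients: 30 Thunderbeat and 30 conventional".

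**The concern.** Maximum-likelihood logistic regression needs enough patients in the smaller outcome class (events or non-events) for each parameter fitted. When there are too few, a true effect is overestimated on average, the estimate varies widely from sample to sample, and a covariate pattern may separate the outcomes so that no finite estimate exists.

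Morbidity is part of the primary objective in Section 2.1 and a secondary objective in Section 9.1. The logistic odds ratios are the only between-arm morbidity estimates with confidence intervals in Section 9.4. The chi-square test yields a p-value, and the intervals promised for complication incidences are not between-arm effects. An unstable odds ratio could therefore become the trial's headline statement on morbidity.

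**Working it through.** **The plan's own figure.** There is none for the morbidity models. The 60 patients come from the blood-loss calculation, which cannot be reproduced because Section 9.3 gives no mean or SD.

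**Step 1: information available.** From Section 9.3, N = 60 (30 + 30). Event rates p are assumed. The smaller class is 60 × min(p, 1 − p). A common guide is 10 per parameter, with treatment counted as one. Treatment plus five covariates is six parameters.

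| Rate p | Smaller class | Parameters supported (÷ 10) | Per parameter with six (÷ 6) |
|---|---|---|---|
| 15% | 9 | 0.9 | 1.5 |
| 25% | 15 | 1.5 | 2.5 |
| 35% | 21 | 2.1 | 3.5 |
| 50% | 30 | 3.0 | 5.0 |

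**Step 2: simulation, no device effect.** Model: logit P(Y = 1) = a + b·group + Σ cⱼxⱼ, 30 v 30. Assumptions: independent standard-normal covariates fixed in advance, log OR 0.35 per SD. Firth regression maximises log L + ½ log|I|, where I is the information matrix. Ranges cover separate runs of about 1,500 to 4,000 trials per setting. Share of trials with an estimated OR above 3 or below 1/3:

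| Model | 15% | 25% | 35% |
|---|---|---|---|
| Unadjusted | 18% | 8% | 6% |
| Ordinary, 1 covariate | 19–20% | 10% | 6–7% |
| Ordinary, 5 covariates | about 30% | 16–18% | 12–14% |
| Firth, 5 covariates | 17–18% | 9–11% | 7–8% |
| Firth, 1 covariate | 14% | 7% | about 5% |

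The two five-covariate rows isolate the estimator. On the log OR scale, root mean squared error with five covariates falls from 1.34 to 0.89 at 15% and from 0.81 to 0.66 at 25% when Firth replaces ordinary regression.

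**Step 3: simulation, true effect.**
- True OR 2, five covariates: median ordinary estimate about 2.2–2.4; Firth 1.9–2.0.
- True OR 0.5 (log OR −0.693), covariate log ORs 0 or 0.5, rates 15%, 25% and 50%: the ordinary mean log OR corresponds to 0.47–0.48 with two covariates, 0.42–0.46 with five and 0.31–0.43 with eight.
- Worked example at 50%, five covariates with coefficient 0.5: ordinary mean −0.817, exp(−0.817) = 0.44; Firth mean −0.695, exp(−0.695) = 0.50.
- Worst case (15%, eight prognostic covariates): 16.5% of fits separated or did not converge.

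**Step 4: test size at nominal 5%, five covariates.** Likelihood-ratio tests rejected in about 6–10% of null trials. Wald tests, which match the usual 95% CI, rejected in 3.3–6.3%. Simulation error at 2,500 runs is 1.96 × √(0.05 × 0.95/2500) ≈ 0.9 points. Under the null the log OR showed no systematic shift.

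**The case against.** The strongest reply is that the plan gives neither a covariate count nor a morbidity rate, so harm cannot be read off it as a fact. That stands: with two covariates, 0.47–0.48 against a true 0.50 is a small bias.

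Three stronger readings are tempting, and the material does not support them.

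- **The device will look effective, or harmful, when it is neither.** Under the null the estimate is centred on 1. The problem there is spread, much of which comes from having only 60 patients: even the unadjusted OR is extreme in 18%, 8% and 6% of null trials. With five covariates, an extreme OR whose Wald interval also excluded 1 occurred in only 3.4%, 5.7% and 5.4%, so the reported interval would usually show the imprecision.
- **The test is too liberal.** Section 9.4 names no test for these models. Only the likelihood-ratio test is liberal; at a 15% rate the Wald test tends to be conservative.
- **Firth alone explains the gain from five ordinary covariates to one Firth covariate.** That comparison changes two things. At 25% and 35%, cutting to one covariate with ordinary regression already removes most of the excess.

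It may also be said that Section 9.4 calls the analysis descriptive, and that its unadjusted chi-square comparison is well calibrated (4.2–5.7% under the null). The second part is true and limits the damage. The first helps less: the same section sets a significance threshold ("Two-tailed *P* values 0.05 will be considered statistically significant"), and an unstable estimate misleads as a description too.

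**Conclusion.** The point holds in conditional form. If about five covariates enter, as a search for confounders could easily produce, ordinary logistic regression exaggerates a true effect (OR 2 read as about 2.2–2.4) and yields extreme null estimates clearly more often than Firth regression with the same covariates. Separation becomes possible at low rates. With one or two covariates the bias is small.

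This goes beyond missing detail, because the covariates in these simulations were fixed in advance. Listing five covariates beforehand would not cure the problem; their number and the estimator both matter.

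The size rests on assumed event rates, covariate effects and covariate counts, none of which the documents give. Any-grade morbidity, if nearer 50%, is less affected than major morbidity. The blood-loss comparison is untouched. The change should be made, but the trial does not stand or fall on it.

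**What to change.** In Section 9.4, for the two morbidity models only:

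1. Fit Firth penalised-likelihood logistic regression, with profile penalised-likelihood 95% intervals and tests.
2. Include randomized group plus only one or two baseline covariates, named before the data are seen. One or two is a judgement in line with the table above, not a sharp limit.
3. Report the risk difference between arms with a 95% CI beside the odds ratio.
4. Amend the SPSS 20.0 sentence to name software that fits this model.

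Linear regression can stay for the continuous outcomes. Little validity is lost by dropping covariates: Section 9.2 plans "block randomization with random block sizes in a 1:1 allocation ratio", so imbalance between arms at baseline arises only by chance.

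The cost is fewer covariates in the morbidity models, slightly shrunken odds ratios (median 1.9–2.0 for a true 2) and probably a second software package. No extra patients or data are needed.

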2.0 OBJECTIVES

2.1 Primary Objective

This is a prospective observational feasibility/QI registry trial to evaluate operative blood loss and post-operative morbidity following use of the Thunderbeat™ device during the Whipple procedure. This will be compared to patients whose Whipple procedure will be performed using conventional dissection and hemostasis techniques.

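### In a randomized trial, section 9.4 uses the regression models to look for confounders; this leaves the adjusted results open to after-the-fact covariate choice, and the plan does not say whether the adjusted or unadjusted result decides

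*Combined protocol and SAP*

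**What the plan says.** Section 9.2 describes "unistratified block randomization with random block sizes in a 1:1 allocation ratio" and gives its purpose: "To achieve comparable groups for known and unknown risk factors randomization will be performed". Section 5.2 also randomizes. Section 2.1, however, introduces the study with the words "This is a prospective observational feasibility/QI registry trial".

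Section 9.4 has two layers of analysis. The arms are first compared without adjustment, by t-test, Mann-Whitney or chi-square. Regression models then follow for blood loss (the primary endpoint), operative time, any and major morbidity, and length of stay, "to examine the relationship between intervention groups and examined outcomes and to identify potential confounders". Their results are all to be given as odds ratios.

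The document does not list covariates, give a selection rule, restrict candidates to values known before allocation, or say which layer is decisive. Baseline data are collected: sex and date of birth (section 4.1), demographics, clinical characteristics and history (section 7.0), and height, weight, gender, Karnofsky status and medications (Appendix B).

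**The concern.** Under randomization, any baseline difference between arms is due to chance. A search for confounders therefore answers a question the design has already dealt with. It adds no protection against bias, and it makes the adjusted treatment effect depend on which variables were picked. If the choice is made with outcomes in view, the nominal p-value and confidence interval no longer describe the procedure actually followed.

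The wording also allows variables that the device may itself affect. Operative time could enter the blood-loss model, and blood loss, transfusion or conversion could enter the morbidity and length-of-stay models. Section 3.1 admits open and laparoscopic cases, so an analyst could adjust for approach as performed, which includes conversions made after allocation. Adjusting for such a variable can remove part of the effect under study.

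The primary endpoint is among the modelled outcomes, so two blood-loss results will exist with no rule for which one counts.

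**Working it through.** **Inputs from the plan.** Section 9.3: "The total expected enrollment is 60 patients: 30 Thunderbeat and 30 conventional"; "alpha error set at 0.05, power>80 percent"; "assumption of difference of 20 percent in blood loss in favor of the Thunderbeat™ device". Section 9.4: "Two-tailed *P* values 0.05 will be considered statistically significant". The SD of blood loss, the R² of baseline covariates and the morbidity rate are not given. Values used for them below are assumptions.

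**1. The plan's own figure.** The 60 cannot be reproduced without an SD; it can only be inverted. With 30 per arm, two-sided 0.05 and 80% power (normal approximation):

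δ/SD = (1.960 + 0.842) × √(2/30) = 0.723, so SD/control mean (CV) = 0.20/0.723 = 0.28.

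The exact t-test needs CV ≤ 0.272 (d = 0.736). At a CV of 0.50, power is 34%.

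**2. Type I error of the adjusted result.** These are simulated trials of 30 v 30 with no true effect and 2,000-4,000 runs per setting (Monte Carlo SE √(0.05 × 0.95/4000) = 0.3 points, or 0.5 points at 2,000). The selection rules and candidate numbers are assumed; the plan names none.

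| How covariates are chosen | Type I error |
|---|---|
| Fixed list | 4.3-5.5% |
| Univariable screen, p<0.05 or p<0.20 | 4.3-5.2% |
| 10% change-in-estimate rule | 4.8-6.4% |
| Backward elimination at P>0.10, 10-15 candidates | about 6-8% (5.8-7.3% and 6.5-7.9% in two sets of runs) |
| Free choice among models, smallest p reported | 8.5-13.1% |

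Unadjusted tests in the same runs gave 4.4-5.6%.

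**3. What fixed adjustment gains or costs (linear models).** Relative to the unadjusted analysis, the SE is multiplied by

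√[(1 − R²) × (1 + k/(N − k − 3))], with k covariates and N = 60.

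- k = 3: the second factor is 1 + 3/54 = 1.056. Break-even R² = 1 − 1/1.056 = 0.05.
- k = 4: the second factor is 1 + 4/53 = 1.075. Break-even R² = 1 − 1/1.075 = 0.07. At R² = 0 the SE rises by 3.7%.

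Power with three covariates and d = 0.736, where the unadjusted t-test has 80%:

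| Joint R² (assumed) | Power |
|---|---|
| 0 | 77.8% |
| 0.10 | 81.9% |
| 0.30 | 90.3% |

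In simulation at the design effect of 0.723 (unadjusted about 79%), four useless covariates reduced power to about 76%. With four truly prognostic covariates, a fixed model had 84% at R² = 0.20 and about 89% at 0.30. Covariates selected from the data gave 79-81% and 83-86%. The simulated fixed list was the correct one, so this is a best case.

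**4. Major morbidity (logistic).** At an assumed 20-40% rate, 60 patients give 12-24 events, which supports one or two covariates. With an assumed control risk of 30% and a true odds ratio of 0.50, the treated-arm risk is 0.214/1.214 = 17.6%, and expected events are 30 × 0.30 + 30 × 0.176 = 14.3. The average estimated odds ratio was 0.47, 0.47, 0.42 and 0.39 with 0, 2, 6 and 10 covariates.

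**The case against.** The strongest reply is that the main comparison is not touched. The unadjusted tests come first, and no covariate choice affects them. Section 9.4 calls the analysis descriptive and section 2.1 calls the study a feasibility one, so the regressions could be read as supplementary. No selection procedure is named, so any inflation figure depends on a rule the reviewer supplies, and under the simplest rule there is essentially no inflation.

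Most of this stands. A reader might infer that the trial's blood-loss comparison has an inflated error rate; the documents do not support that while the unadjusted tests remain. Nor do they say that stepwise selection will be used or that post-allocation variables will be entered. They only leave both open. The drift in the logistic odds ratio comes from the number of covariates, not from selecting them, and a fixed list of ten would drift too.

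The descriptive label is a weaker defence. Section 9.1 sets out to determine whether the device reduces blood loss, section 9.3 gives an alpha and a power, and section 9.4 sets a significance threshold. With two results for the primary endpoint and no stated priority, the adjusted one could become the headline.

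**Conclusion.** The point holds as a pre-specification fault in the adjusted analyses, with an inexpensive and better alternative. The confounder search does not fit the randomized design, the adjustment set is open, post-allocation variables are not excluded, and the deciding analysis is not named.

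The size is modest. Under the assumed rules, the adjusted result's type I error runs from nominal to about 8% for a single automatic procedure, and reaches 8.5-13% only with free choice among models.

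It is also tempting to conclude that fixed adjustment is bound to be more precise. The documents do not support that. They give no R², and Karnofsky status, limited to 80 or above by section 3.1, can take only three values. The gain needs a joint R² above about 0.05-0.07, applies to the linear models, and starts from an 80% power that cannot be verified without an SD. At a CV of 0.50, an R² of 0.10-0.30 would raise power only from 34% to 37-46%, before any charge for estimating the covariates.

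**What to change.** In section 9.4:

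- Delete the clause on identifying confounders.
- State whether the unadjusted or the adjusted comparison is primary, and label the other as supportive.
- Fit each linear model with arm plus two or three pre-randomization variables already collected (for example age, sex, and BMI from height and weight). Fix the list before outcomes are examined, and keep each variable whatever its significance or imbalance.
- Allow no covariate measured after allocation.
- Report any and major morbidity unadjusted, or with at most one fixed baseline covariate.
- Analyse blood loss and length of stay on a log scale if skewed, deciding this without reference to arm. Report mean differences or ratios with 95% confidence intervals from the linear models, and keep odds ratios for the logistic ones.

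In section 2.1, describe the design as randomized so that it agrees with sections 5.2 and 9.2.

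The cost is a few sentences and no new data. The downside is that covariates that turn out not to be prognostic cost about 2-4 points of power, which is a reason to keep the list short. Adjustment does not make up for the missing SD in section 9.3.

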APPENDIX A: Karnofsky Performance Scale

Description	Percent(%)
Normal; no complaints; no evidence of disease	100
Able to carry on normal activity; minor signs and symptoms of disease	90
Normal activity with effort; some signs and symptoms of disease	80
Cares for self; unable to carry on normal activity or do work	70
Requires occasional assistance, but is able to care for most personal needs	60
Requires considerable assistance and frequent medical care	50
Disabled; requires special care and assistance	40
Severely disabled; hospitalization indicated although death not imminent	30
Very sick; hospitalization necessary; requires active support treatment	20
Moribund; fatal processes progressing rapidly	10
Dead	0

APPENDIX B: STUDY VISIT SCHEDULE

	Baseline	Intervention	Follow-Up		
	Screening ²	Day of Surgery	Hospital Discharge	30 Day Post-Op Visit ³	90 Day Status ⁵
Past medical history ¹	X				
Informed consent	X				
Physical exam ⁴	X				
Operating time from skin incision to closure (mins)		X			
Anesthesia time (mins)		X			
Intraoperative estimated blood loss (cc)		X			
Administration of blood products		X	X		
Peri and postoperative complications		X	X	X	X
Hospital length of stay			X		
Mortality			X	X	X

¹Study-relevant past medical and surgical history

²Screening procedures to be completed within 60 days of surgery.

³To be performed 30 days from day of surgery \pm 14 days.

⁴Baseline height, weight, gender, karnofsky performance status, medications from pre-surgical physical examination

⁵Medical records (inpatient and outpatient) will be reviewed by a study team member for additional postoperative complications. No direct contact or clinic visit required.
